8. STUDY DRUG MANAGEMENT

8.1. Description of ABI-009

8.1.1. ABI-009 Packaging, Labeling, and Storage

ABI-009 will be supplied by the Sponsor in single-use vials as lyophilized product. Each single-use 50-mL vial will contain 100 mg sirolimus and human albumin as a stabilizer. Each vial will be labeled according to country-specific regulatory requirements for labeling of IPs.

Unopened vials of ABI-009 should be stored in a refrigerator (2°-8°C; 36°-46°F) in original cartons to protect from light. Reconstituted ABI-009 may be stored for up to 4 hours at 2-8°C (36°- 46°F), followed by 4 hours at room temperature (<25°C) in the IV bag. Both unopened vials of ABI-009 and reconstituted ABI-009 should be stored in an area free of environmental extremes and must be accessible only to study personnel.

Temperature records for ABI-009 must be made available to Aadi or Sponsor nominated Contract Research Organization monitoring teams for verification of proper study drug storage.

8.2. ABI-009 Accountability, Disposal, and Compliance

Only completely unused study drug vials should be retained by the site until a representative from Aadi or Sponsor-nominated CRO has completed an inventory. Partially used and completely used vials should be destroyed according to the site's guidelines, and their disposition should be recorded on the Investigational Drug Accountability Record Form.

The Investigator, or designee, shall record the dispensing of study drug to patients and any remaining study drug after dosing in a study drug accountability record. The study drug record will be made available to Aadi or authorized Aadi-designated monitoring personnel for the purpose of accounting for the study drug supply. Inspections of the study drug supply for inventory purposes and assurance of proper storage will be conducted as necessary. Any significant discrepancy will be recorded and reported to Aadi or their designee and a plan for resolution will be documented.

Accurate recording of all ABI-009 administration will be made in the appropriate section of the patient's eCRF and source documents. The investigator or designee is responsible for accounting for all study-specific IP either administered or in their custody during the course of the study.

8.3. ABI-009 Reconstitution

NOTE: It is not a requirement to use filter needles in the preparation, or in-line filters during the administration of ABI-009. In any event, filters of pore size less than 15 microns (15 µm) must not be used.

ABI-009 will be reconstituted by appropriate study personnel following the Pharmacy Manual, and administered to the patient in the study site. The Investigator will calculate the BSA of the patient in order to determine the total amount of ABI-009 to be administered.

8.4. Receipt and Return of ABI-009

Upon receipt of the study drug supplies, the Investigator or designee will conduct an inventory and sign both copies of the study drug receipt and forward one copy to the address indicated on the form. One copy of the receipt and the packing slip must be retained in the Investigator's regulatory file records.

A representative from Aadi or his/her designee will inspect the study drug inventory, Drug Accountability Record form(s), and will arrange for the disposition of any remaining unused study drug. No study drug may be returned to Aadi without the representative from Aadi or other Aadi-designated personnel first inspecting the study drug inventory and accountability documentation.

9. CONCOMITANT MEDICATIONS AND PROCEDURES

All concomitant treatments, including blood and blood products, must be reported on the eCRF. Throughout the study, investigators may prescribe any concomitant medications or treatments deemed necessary to provide adequate supportive care except for those listed in [Section 9.2](#).

Concomitant therapies are to be collected from enrollment/randomization through the EOT Visit. Therapy name including indication, dose, frequency, route, start date and stop date will be recorded on each patient's eCRF(s).

9.1. Permitted Medications and Procedures

The investigator must be informed as soon as possible about any medication taken from the time of screening until the end of the clinical phase of the study (final study visit). Any concomitant medication(s), including herbal preparations, taken during the study will be recorded in the eCRF. The minimum requirement is that drug name, dose, and the dates of administration are to be recorded. Additionally, a complete list of all prior cancer therapies will be recorded in the eCRF.

Patients should receive full supportive care during the study, including transfusions of blood and blood products, and treatment with antibiotics, anti-emetics, anti-diarrheas, and analgesics, and other care as deemed appropriate, and in accordance with their institutional guidelines. WBC growth factors may be administered at the discretion of the investigator, consistent with institutional guidelines.

Extreme precaution must be taken with contraceptives (either combined or progesterone only), as it is not known if there is the potential of inhibition/induction of enzymes that affect the metabolism of estrogens and/or progestins.

9.2. Prohibited Medications and Procedures

The use of certain medications, and illicit drugs within 5 half-lives or 28 days, whichever is shorter prior to the first dose of study drug and for the duration of the study will not be allowed. If a prohibited medication is required for single use (such as for a procedure) while study drug is held, the Aadi medical monitor can approve such use.

The following medications or non-drug therapies are prohibited:

- Other anti-cancer therapy while on treatment in this study.
- Antiretroviral drugs (patients with known HIV are ineligible for study participation).
- Herbal remedies (eg, St. John's wort) unless approval is granted by the medical monitor.
- Sirolimus is metabolized primarily by CYP3A4. Drugs that are strong inhibitors or inducers of CYP3A4 may only be used under special circumstances (eg, as a single use for a procedure) while treatment with study drug is interrupted. The list may be modified based on emerging data.
- Use of any known CYP3A4 substrates with narrow therapeutic window (such as fentanyl, alfentanil, astemizole, cisapride, dihydroergotamine, pimozide, quinidine,

terfanide) within the 14 days prior to receiving the first dose of ABI-009. Other medications may be allowed if there is agreement between the sponsor and investigator

- Use of strong inhibitors and inducers of CYP3A4 within the 14 days prior to receiving the first dose of ABI-009

9.3. Drug-Drug Interactions of ABI-009 and Standard PAH Medications

The potential for drug-drug interactions between ABI-009 and standard PAH medications is low. Sirolimus is a substrate for (i.e., it is metabolized by) both cytochrome P-450 3A4 (CYP3A4) and p-glycoprotein (P-gp). It is not an inducer or inhibitor of CYP3A4 or P-gp. Several of the standard PAH medications, eg, bosentan, sildenafil, ambrisentan, treprostinil etc are also metabolized primarily by CYP3A4. Since none of these medications are strong inducers or inhibitors of CYP3A4, they are used in together in combination for treatment of PAH. Therefore, addition of ABI-009 to standard PAH therapy is not expected to alter the PK of these drugs or cause adverse drug interactions. Nevertheless, in the planned clinical study the starting dose is 10X below the MTD determined in an oncology phase 1 study, giving a very wide safety margin for the patients. Additionally, safety will be closely monitored along with the PK of sirolimus in the PAH phase 1 study, and it may be possible to identify if any AE is related to drug interactions through analysis of sirolimus plasma levels.

10. STATISTICAL CONSIDERATIONS

10.1. Study Endpoints

Primary Endpoints:

MTD, DLTs, and toxicities and safety profile of 16 weeks, as well as safety profile of the up to 48 weeks of ABI-009 given IV, in patients with PAH who are WHO Functional Class II or III despite best available background therapy.

In the dose-finding portion of the study, 4 dose levels of ABI-009 will be tested in cohorts of 3 patients each (1, 2.5, 5, and 7.5 mg/m²), using the 3+3 dose escalation design. There will be no intra-patient dose escalation allowed. Escalation to the next dose level with a new cohort of 3 patients will occur after no DLT was observed in the first treatment cycle of 4 weeks. If a DLT occurs in a cohort, additional 3 patients will be recruited to the cohort. If no further DLTs occur, then a new cohort of 3 patients at the next higher dose level can be enrolled. If 2/6 patients at dose level 1a experience a DLT, then that cohort will be closed to further enrollment and the study may be terminated. If 2/6 patients at dose levels 2a or 3a experience a DLT, then the previous dose level is considered the MTD.

The treated population will be the analysis population for all safety analyses. Adverse events will be coded using the Medical Dictionary for Medical Activities (MedDRA) and grouped by their system organ class and preferred term. Summary tables will include the number and percentage of treatment-emergent and treatment-related AEs, AEs of special interest, SAEs, and incidence of patients experiencing dose modifications, dose delay/dose not given, dose interruptions, and/or premature discontinuation of IP due to an AE.

An external Safety Monitoring Committee (SMC) will assess safety data periodically as needed.

Secondary Endpoint(s):

The following will be measurements will be summarized at baseline and at 17 weeks (after 16 weeks of treatment in the Dose-finding Safety Part):

- pulmonary vascular resistance (PVR) by right heart catheterization
- pulmonary artery pressure (PAP)
- pulmonary capillary wedge pressure (PCWP)
- central venous pressure (CVP)

The following will be measurements will be summarized at baseline, 5, 9, 13, and 17 weeks:

- Doppler-echocardiographic assessments of right ventricular structure and function
- 6-minute walk distance (6MWD)
- WHO functional class
- Pulmonary function test

The following will be measurements will be summarized every 8 weeks of the Extension Part (ie, at week E9, E17, E25, and E33):

- 6MWD
- WHO Functional Class
- Pulmonary function test

Exploratory Endpoint(s):

- Pharmacokinetic (PK) profile and trough level of sirolimus for weekly treatment during the 16 weeks of Dose-finding Safety Part and every other week treatment during the Extension Part
- Measurement of brain natriuretic peptide (BNP), C-reactive protein (CRP) and troponin levels, indicative of right ventricular strain at baseline, 5, 9, 13, and 17 weeks and for BNP, every 8 weeks in the optional Extension Part (E9, E17, E25, E33)
- Change from baseline to week 17 and to weeks E17 and E33 in the Extension Part in 36-Item Short Form Health Survey (SF-36) physical functioning scale
- Change from baseline to week 17 and to weeks E17 and E33 in the Extension Part in emPHasis10 questionnaire

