Study Treatments	
This phase 1/1b study will have a 16-week Dose-finding Safety Part to identify recommended phase 2 dose and evaluate the safety and efficacy profile of weekly ABI-009 (via dose-finding and dose-expansion cohorts), followed by an optional 32-week Extension Part to obtain additional safety and efficacy data on longer term treatment with ABI-009.
 
16 weeks of Dose-finding Safety Part
 
In the dose-finding phase 1 portion of the study, 4 dose levels of ABI-009 will be tested in cohorts of 3 patients each (1, 2.5, 5, and 7.5 mg/m², see Table 1), using the 3+3 dose escalation design. There will be no intra-patient dose escalation allowed. Escalation to the next dose level with a new cohort of 3 patients will occur after no DLT was observed in the first treatment cycle of 4 weeks. If a DLT occurs in a cohort, additional 3 patients will be recruited to the cohort. If no further DLTs occur, then a new cohort of 3 patients at the next higher dose level can be enrolled. If 2/6 patients at dose level 1a experience a DLT, then that cohort will be closed to further enrollment and the study may be

	
terminated. If 2/6 patients at dose levels 2a, 3a, or 4a experience a DLT, then the previous dose level is considered the MTD.
 
It is estimated that a maximum of up to 24 patients will be required to achieve the MTD; however, MTD could be reached with as few as 9 patients. Patients will be allowed to dose reduce by one dose level for reasons of toxicity, with a maximum of 2 dose reductions allowed for a patient. At the lowest dose level, a dose reduction of 25% will be allowed.
										
Table 1: Doses of ABI-009 Given Weekly											
	

Dose Level	1a	2a	3a	4a	

ABI-009 Weekly Dose (mg/m²)	1	2.5	5	7.5	

	Dose Level	1a	2a	3a	4a	ABI-009 Weekly Dose (mg/m²)	1	2.5	5	7.5
Dose Level	1a	2a	3a	4a							
ABI-009 Weekly Dose (mg/m²)	1	2.5	5	7.5							

Note: The original protocol (dated December 10, 2015) included dose levels 1 (10 mg/m²), 2, (20 mg/m²) and 3 (30 mg/m²), and dose level -1 (5 mg/m²).
 
After the MTD is reached, in phase 1b, there may be up to 2 cohort expansions at the MTD and/or one alternate dose or schedule to determine the recommended phase 2 dose.
											
Optional 32-week Extension Part											

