7. DESCRIPTION OF STUDY TREATMENTS

7.1. ABI-009 Dosage, Administration, and Schedule

The planned treatment period is 16 weeks, with ABI-009 given weekly. Patients, who based on the investigator and Safety Committee's assessment, tolerate ABI-009 and show clinical benefit during the 16-week Dose-finding Safety Part, and for whom there are no alternative therapies available, may opt to continue therapy in the optional Extension Part, with ABI-009 given weekly at the originally assigned dose (or lower, if permanently reduced) for up to 32 additional weeks. A physician must be available at the time of administration of IP on dosing days that correspond to study visits. Supportive care per the institution's normal standard of care including concomitant medications can be provided at the investigator's discretion.

In the dose-finding portion of the study, 4 dose levels of ABI-009 will be tested in cohorts of 3 patients each (1, 2.5, 5, and 7.5 mg/m², see [Table 1](#) and below), using the 3+3 dose escalation de-escalation design. There will be no intra-patient dose escalation allowed. Escalation to the next dose level with a new cohort of 3 patients will occur after no DLT was observed in the first treatment cycle of 4 weeks. If a DLT occurs in a cohort, additional 3 patients will be recruited to the cohort. If no further DLTs occur, then a new cohort of 3 patients at the next higher dose level can be enrolled. If 2/6 patients at dose level 1a experience a DLT, then that cohort will be closed to further enrollment and the study may be terminated. If 2/6 patients at dose levels 2a, 3a, or 4a experience a DLT, then the previous dose level is considered the MTD.

It is estimated that a maximum of up to 24 patients will be required to achieve the MTD; however, MTD could be reached with as few as 9 patients. Patients will be allowed to dose reduce by one dose level for reasons of toxicity, with a maximum of 2 dose reductions allowed for a patient. At the lowest dose level, a dose reduction of 25% will be allowed.

Dose Level	1a	2a	3a	4a
ABI-009 Weekly Dose (mg/m ²)	1	2.5	5	7.5

Note: The original protocol included dose levels 1 (10 mg/m²), 2, (20 mg/m²) and 3 (30 mg/m²), and dose level -1 (5 mg/m²).

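### The 3+3 rules disagree between sections on levels and patient numbers, name no MTD if the top level is cleared, and are ambiguous for two or more DLTs in the first three patients

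*Combined protocol and SAP*

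**What the plan says.** The current design has four dose levels, 1a to 4a (Table 1), tested in cohorts of three, with DLTs counted over the first four-week cycle. Section 10.1 gives these rules:

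- No DLT: "Escalation to the next dose level with a new cohort of 3 patients will occur after no DLT was observed".
- After a DLT: "If a DLT occurs in a cohort, additional 3 patients will be recruited to the cohort".
- After that expansion: "If no further DLTs occur, then a new cohort of 3 patients at the next higher dose level can be enrolled".
- Failure at the lowest level: "If 2/6 patients at dose level 1a experience a DLT, then that cohort will be closed to further enrollment", and the study may then be stopped.
- Naming the MTD: "If 2/6 patients at dose levels 2a or 3a experience a DLT, then the previous dose level is considered the MTD".

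The synopsis (Study Treatments) and section 7.1 repeat these rules but word the last one differently: "If 2/6 patients at dose levels 2a, 3a, or 4a experience a DLT, then the previous dose level is considered the MTD".

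On size, section 7.1 says that "a maximum of up to 24 patients will be required to achieve the MTD" and that "MTD could be reached with as few as 9 patients". Section 10.2 and the synopsis (Statistical Considerations) also give 24 and 9. Both call the planned levels three, yet build the 24 from four levels. The synopsis schema gives up to 18 patients beside four doses.

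The synopsis (Sample Size) and sections 3.1 and 4.1 call the design a standard 3+3. Section 7.1 alone adds de-escalation to the label.

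The MTD is a primary endpoint (synopsis, 2.2, 10.1). The phase 1b expansions are placed after the MTD is reached, achieved or identified (synopsis objectives, treatments, statistics and schema; 2.1; 10.2).

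**The concern.** A 3+3 design is defined by its decision rules, and the MTD is whatever those rules return. Three features look wrong.

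1. The sections do not describe the same trial: they differ in the number of levels, in the maximum number of patients, and in whether the MTD rule covers 4a.
2. The rules give an outcome for failing the bottom level but none for clearing the top one.
3. It is not clear what happens when two or three of the first three patients have a DLT.

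For those outcomes, what is reported as the MTD, whether three more patients are exposed, and when phase 1b may open would be settled after the data are seen. Two sites could also apply the text differently.

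**Working it through.** **1. Reproducing the plan's counts**

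- Maximum, four levels filled to six: 4 × 6 = 24. This matches the text.
- Schema: 18 = 3 × 6. It fits three levels, not the four doses printed beside it.
- Expansion of 4 to 7 patients to reach 10: 10 − 6 = 4 and 10 − 3 = 7. A level entering phase 1b is therefore expected to hold three or six patients already.
- Minimum of 9: 3 at 1a + 6 at 2a = 9 (see step 3 for the alternatives).

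Section 3.2 mentions that the 7.5 mg/m² cohort was added. The three-level wording, the 18, and the missing 4a in section 10.1 are all consistent with text not updated at that point.

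**2. Tracing each result at 4a**

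| Result at 4a | Synopsis and 7.1 | 10.1 |
|---|---|---|
| 2/6 | Level below is the MTD | No rule (4a not listed) |
| 0/3 | Go to next level; none exists | Same |
| 1/6 | Go to next higher level; none exists | Same |

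A failed 4a thus has an outcome in two places and none in the third. A cleared 4a has none anywhere. It would be reached with 4 × 3 = 12 to 4 × 6 = 24 patients.

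How likely is clearance? The documents give no DLT rates, so the rates below are assumptions that show a range only. With DLT rate p at a level, and clearance meaning 0/3 or 1/6:

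P(clear level) = (1 − p)³ + 3p(1 − p)⁵

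P(4a cleared) is the product over the four levels. The share of clearances resting on 0/3 is (1 − p)³ ÷ P(clear level) at 4a.

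| Assumed rates, 1a/2a/3a/4a | P(clear) by level | P(4a cleared) | Share on 0/3 |
|---|---|---|---|
| 5/5/5/5% | 0.973 each | 0.898 | 0.881 |
| 5/10/15/20% | 0.973, 0.906, 0.814, 0.709 | 0.509 | 0.723 |
| 5/10/20/35% | 0.973, 0.906, 0.709, 0.396 | 0.248 | 0.693 |
| 10/20/30/40% | 0.906, 0.709, 0.494, 0.309 | 0.098 | 0.698 |

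Worked line, p = 20%: 0.8³ + 3(0.2)(0.8⁵) = 0.512 + 0.197 = 0.709, and 0.512 ÷ 0.709 = 0.72. These figures are the same whether 2/3 stops a level at once or is first expanded and then fails as 2/6.

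**3. Two or more DLTs in the first three**

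| Meaning given to the expansion trigger | 2/3 in the first three | Then 0/3 in the next three |
|---|---|---|
| At least one DLT | Three more are added | Meets the no-further-DLTs sentence (a higher level may open) and the 2/6 sentence (1a closes, or the level below is the MTD) |
| Exactly one DLT | No action written | Does not arise under a written rule |

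On the first reading, the two actions compete only at 1a to 3a, since nothing lies above 4a. On that reading alone, the chance of 2/3 then 0/3 at a level is 3p²(1 − p) × (1 − p)³: 0.6% at p = 5%, 2.0% at 10%, 4.9% at 20% and 6.5% at 30%.

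The stated minimum does not decide between the readings. Filling a failing level to six gives 3 + 6 = 9. Stopping at 2/3 gives 3 + 3 = 6, but filling the lower level to six afterwards gives 6 + 3 = 9 again.

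**The case against.** The best reply is that this is called a standard 3+3, so convention fills the gaps, and that little depends on the MTD itself. The recommended phase 2 dose may differ from the MTD and draws on safety, efficacy, pharmacologic and correlative results. Expansion may be at the MTD and/or an alternate dose or schedule. An external safety committee reviews the data. The 24-patient statement shows that the sponsor expected escalation to end with an MTD by the time 4a is complete. The wrong counts are plainly leftovers. The opening of a higher level is worded as permission, while the 2/6 sentence is directive, so the latter may be meant to govern.

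Much of this stands. It limits the consequences and makes the count errors editorial. It does not close the gaps. No available text says which level is the MTD after a cleared 4a, or whether 0/3 is enough. The alternate-dose option still comes after the MTD. Section 10.1 has the committee assess safety data as needed and does not give it the MTD decision. No sentence ranks the two competing rules.

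A reader might infer that 2/3 then 0/3 is a flat contradiction. The documents do not support that, because it depends on reading the trigger as at least one DLT; on the other reading it is an omission. A reader might also infer that failure at 4a is undefined. It is not, since the synopsis and section 7.1 cover it; the fault there is that section 10.1 differs.

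**Conclusion.** The escalation rules are inconsistent and incomplete as written, and should be corrected. The conflicts over levels covered, number of levels and maximum N can be read directly from the text. The absence of an MTD after a cleared 4a follows from the rules. The 2/3 problem is an ambiguity.

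Clearing 4a has a probability of about 10% to 90% under the assumed rates. That shows it cannot be dismissed as remote, and no more; it is not a forecast.

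A reader might go further and conclude that the primary endpoint fails or that phase 1b could not proceed usefully. The documents do not support that: DLT and safety results would still be reported, and a recommended phase 2 dose that may differ from the MTD would still be available. What would be undefined is the MTD component and the written trigger for expansion.

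Some background text (by the table of contents, apparently including sections 1.2.3.5 and 1.2.3.8) and the Figure 9 image were not available, so the absence is judged on the remaining text.

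**What to change.** Reconcile the synopsis (Sample Size, schema, Study Treatments, Statistical Considerations) with sections 7.1, 10.1 and 10.2, so that the number of levels, the minimum and maximum N, the design label and the levels covered by the 2/6 rule agree everywhere.

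Have the sponsor state one action for each DLT count in three and in six patients at each level; a single decision table cited by every section would do this. State also what is reported as the MTD if the top level is cleared, on how many patients that rests, and what then opens phase 1b.

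No dose or stopping rule is proposed here; those choices are the sponsor's. The cost is amendment wording. Patient numbers change only if the actions chosen require it.
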